### *PROMIS-Anxiety*

The change from study baseline to Day 90 in anxiety as measured by *PROMIS-Anxiety* is a secondary endpoint. This analysis will compare the treatment groups, separately, to the control group using a MMRM analysis. The repeated measures are the change from baseline *PROMIS-Anxiety* score obtained at Day 15, 30, 60, and 90, respectively. The model will include fixed categorical effects for treatment, week, treatment by week interaction, and the baseline *PROMIS-Anxiety* score as a continuous covariate. We will employ the Stata *xtmixed* command or the R *lmer* function from the *lme4* package with REML and an unstructured within-patient covariance structure for this model. We will evaluate the assumptions of this model, including normality, using residual and other diagnostic plots of model fit.

From this model, we will estimate least squares means, standard errors, treatment differences in least squares means, and 95% confidence intervals for each time point. Primary inference will be based on the treatment comparison of least squares means for Day 90 from this model, and a p-value will be presented for this time period only. The null hypothesis is that the mean difference in the primary endpoint between the experimental arms and the sham arm is zero, versus the alternative hypothesis that this difference is not zero.

### *PCS SF-6*

The change from study baseline to Day 90 in pain catastrophizing as measured by PCS SF-6 is a secondary endpoint. This analysis will compare the treatment groups, separately, to the control group using a MMRM analysis. The repeated measures are the change from baseline PCS SF-6 score obtained for Day 15, 30, 60, and 90, respectively. The model will include fixed categorical effects for treatment, week, treatment by week interaction, and the baseline PCS SF-6 score as a continuous covariate. We will employ the Stata *xtmixed* command or the R *lmer* function from the *lme4* package with REML and an unstructured within-patient covariance structure for this model. We will evaluate the assumptions of this model, including normality, using residual and other diagnostic plots of model fit.

From this model, we will estimate least squares means, standard errors, treatment differences in least squares means, and 95% confidence intervals for each time point. Primary inference will be based on the treatment comparison of least squares means for Day 90 from this model, and a p-value will be presented for this time period only. The null hypothesis is that the mean difference in the primary endpoint between the experimental arms and the sham arm is zero, versus the alternative hypothesis that this difference is not zero.

### *MME*

A key secondary endpoint is the change from study baseline to Day 90 in weekly MME of prescribed medication. Descriptive summary statistics will be presented for weekly MME of prescribed medication at two timepoints: baseline and Day 90. Analysis of this endpoint will compare the difference in weekly MME of prescribed medication between the treatment groups

and control group at baseline and Day 90 using analysis of covariance (ANCOVA), adjusting for baseline MME. We will assess the assumptions underpinning the ANCOVA model graphically and will undertake appropriate transformation of the weekly average MME outcome as deemed appropriate. If no suitable transformations can be found, bootstrapped confidence intervals for the between-group differences in weekly MME will be produced. Both adjusted and unadjusted between-group comparisons will be presented with 95% confidence intervals.

#### 4.6.3 Exploratory Endpoint Analyses

##### PROMIS-PF

The change from study baseline to Day 90 in physical function as measured by PROMIS-PF is an exploratory endpoint. This analysis will compare the treatment groups, separately, to the control group using a MMRM analysis. The repeated measures are the change from baseline PROMIS-PF score obtained for Day 15, 30, 60, and 90, respectively. The model will include fixed categorical effects for treatment, week, treatment by week interaction, and the baseline PROMIS-PF score as a continuous covariate. We will employ the Stata *xtmixed* command or the R *lmer* function from the *lme4* package with REML and an unstructured within-patient covariance structure for this model. We will evaluate the assumptions of this model, including normality, using residual and other diagnostic plots of model fit.

From this model, we will estimate least squares means, standard errors, treatment differences in least squares means, and 95% confidence intervals for each time point. Primary inference will be based on the treatment comparison of least squares means for Day 90 from this model, and a p-value will be presented for this time point only. The null hypothesis is that the mean difference in the primary endpoint between the experimental arms and the sham arm is zero, versus the alternative hypothesis that this difference is not zero.

##### PROMIS-Depression

The change from study baseline to Day 90 in depression as measured by PROMIS-Depression is an exploratory endpoint. This analysis will compare the treatment groups, separately, to the control group using a MMRM analysis. The repeated measures are the change from baseline PROMIS-Depression score obtained for Day 15, 30, 60, and 90, respectively. The model will include fixed categorical effects for treatment, week, treatment by week interaction, and the baseline PROMIS-Depression score as a continuous covariate. We will employ the Stata *xtmixed* command or the R *lmer* function from the *lme4* package with REML and an unstructured within-patient covariance structure for this model. We will evaluate the assumptions of this model, including normality, using residual and other diagnostic plots of model fit.

From this model, we will estimate least squares means, standard errors, treatment differences in least squares means, and 95% confidence intervals for each time point. Primary inference will be based on the treatment comparison of least squares means at Day 90 from this model, and a p-value will be presented for this time point only. The null hypothesis is that the mean difference

in the primary endpoint between the experimental arms and the sham arm is zero, versus the alternative hypothesis that this difference is not zero.

#### *PGIC*

An exploratory endpoint is the change in disease severity as measured by the PGIC at Day 90. This secondary analysis will compare the treatment groups, separately, to the control group using a logistic regression analysis. Based on the PGIC assessment, a dichotomous scale of “Yes” or “No” will be derived. A favorable response of 5-7 on the PGIC indicates “Yes”, significant improvement occurred over the course of the study. An unfavorable response of 1-4 indicates “No”, significant improvement did not occur over the course of the study.

The percentage of patients in each treatment arm responding in the “Yes” and “No” categories will be compared to the percentage of patients in the control arm responding in the “Yes” and “No” categories via the Cochran Mantel-Haenszel test. We will analyze responder status (i.e. “Yes” vs “No” as the dependent variable) using logistic regression, with terms for study-arm and baseline PROMIS-PI.

#### *Biometric Data – Steps*

We will assess the change from study baseline to Day 90 by comparing the treatment groups, separately, to the control group using a MMRM analysis. The repeated measures are the change from baseline weekly steps obtained for all weeks between Baseline and Day 90. The model will include fixed categorical effects for treatment, week, and the baseline weekly steps as a continuous covariate. We will employ the Stata xtmixed command or the R lmer function from the lme4 package with restricted maximum likelihood estimation (REML) and an unstructured within-patient covariance structure for this model. We will evaluate the assumptions of this model, including normality, using residual and other diagnostic plots of model fit.

From this model, we will estimate least squares means, standard errors, treatment differences in least squares means, and 95% confidence intervals for each time point. Primary inference will be based on the treatment comparison of least squares means at Day 90 from this model, and a p-value will be presented for this time point only. The null hypothesis is that the mean difference in the primary endpoint between the experimental arms and the sham arm is zero, versus the alternative hypothesis that this difference is not zero.

#### *Biometric Data – Sleep*

We will assess the change from study baseline to Day 90 by comparing the treatment groups, separately, to the control group using a MMRM analysis. The repeated measures are the change from baseline weekly minutes classified as “sleep” obtained at weekly intervals between baseline and Day 90. The model will include fixed categorical effects for treatment, week, and baseline weekly steps as a continuous covariate. We will employ the Stata xtmixed command or the R lmer function from the lme4 package with restricted maximum likelihood estimation (REML) and an unstructured within-patient covariance structure for this model. We will evaluate the

assumptions of this model, including normality, using residual and other diagnostic plots of model fit.

From this model, we will estimate least squares means, standard errors, treatment differences in least squares means, and 95% confidence intervals for each time point. Primary inference will be based on the treatment comparison of least squares means at Day 90 from this model, and a p-value will be presented for this time point only. The null hypothesis is that the mean difference in the primary endpoint between the experimental arms and the sham arm is zero, versus the alternative hypothesis that this difference is not zero.

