**Objectives:**

Primary Objective:

To assess the efficacy of immersive Skills-Based VR and Distraction VR in improving perceived pain from baseline to Day 30.

Secondary Objective:

To assess the efficacy of immersive Skills-Based VR and Distraction VR in improving perceived pain interference from baseline to Day 60 and Day 90.

To assess the efficacy of Skills-Based and Distraction VR in improving self-reported perceptions of sleep quality, sleep depth, and restoration associated with sleep from baseline to Day 90.

To assess the efficacy of Skills-Based and Distraction VR in improving self-reported perceptions of anxiety from baseline to Day 90.

To assess the efficacy of Skills-Based and Distraction VR in improving self-reported pain catastrophizing from baseline to Day 90.

To assess the efficacy of Skills-Based and Distraction VR in reducing use of opioids from baseline to Day 90.

Tertiary Objectives:

To assess the efficacy of Skills-Based and Distraction VR in improving self-reported physical function from baseline to Day 90.

To assess the efficacy of Skills-Based and Distraction VR in improving self-reported depression from baseline to Day 90.

To assess the efficacy of Skills-Based and Distraction VR via patients' global impression of change (PGIC).

To assess the efficacy of Skills-Based and Distraction VR in improving wearable measures of physical activity from baseline to Day 90.

To assess the efficacy of Skills-Based and Distraction VR in improving wearable measures of sleep quality from baseline to Day 90.

To assess the effect of presence on the efficacy of Skills-Based and Distraction VR in improving measures of pain interference from baseline to Day 30.

To assess the effect of Immersive Tendencies on the efficacy of Skills-Based and Distraction VR in improving measures of pain interference from baseline to Day 30.

To assess the effect of dose on the efficacy of Skills-Based and Distraction VR in improving measures of pain interference from baseline to Day 30.

**Endpoints:** Primary Endpoint: Change in PROMIS Pain Interference  
Secondary Endpoints: Change in PROMIS Sleep Disturbance, PROMIS Anxiety, Pain Catastrophizing, MME usage.

**Study Population:** Individuals ages 13 or older with an ongoing low back-pain problem that has persisted at least 3 months and has resulted in pain on at least half the days in the past 6 months.

**Phase:** Phase 2

[figure not shown]

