To assess the efficacy of Skills-Based and Distraction VR in improving wearable measures of sleep from baseline to Day 90. The objective will be considered achieved if there is statistical evidence of measured improvement in either VR group compared to control (sham) VR.	The change from study baseline to Day 90 in sleep quantity (total minutes asleep as well as "sleep efficiency", see Section 4.6.3 for more info) as measured by FitBit is an exploratory endpoint. Changes in the seconds in sleep will also be examined for interaction effects on the primary outcome.	There is evidence that physical activity can improve mood, sleep, and general health, yet persons with chronic pain may limit their activity because of their pain.  Previous versions of the skills-based program used in this study showed improvements in the sleep subscale of a pain interference measure. 
Exploratory Subanalysis		
To assess subgroup analyses for the change from baseline in PROMIS-PI. An MMRM	The impact of the following variables mentioned in section	See Section 9.4.7 for details.

OBJECTIVES	ENDPOINTS	JUSTIFICATION FOR ENDPOINTS
model will be used to test for treatment by subgroup interactions.	9.4.7 will be assessed to changes in the primary outcome.	

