#### 9.4.9 EXPLORATORY OUTCOMES

A few exploratory hypotheses have been considered:

Exploratory Outcome: Global impression of change with pain treatment using PGIC

Question: Which intervention is associated with patient's perceived change in condition due to treatment?

Dependent variable: patient's perceived change in condition as assessed by PGIC

Comparisons: Superiority for both of the following (1) Distraction VR therapy vs. sham VR therapy; (2) skills-based VR therapy vs. sham VR therapy, if there is a statistically significant difference in Skills based VR vs Sham VR then a third test will be completed (3) Skills-based VR therapy vs Distraction VR therapy

Exploratory Outcome: Quality of sleep over time by biometric data on Fitbit Charge 4 (total minutes asleep and sleep efficiency per night)

Hypothesis: Skills-based VR will lead to a greater improvement in sleep quality than distraction based VR or Sham VR.

Comparisons: Superiority for both of the following (1) Distraction VR therapy vs. sham VR therapy; (2) skills-based VR therapy vs. sham VR therapy, if there is a statistically significant difference in Skills based VR vs Sham VR then a third test will be completed (3) Skills-based VR therapy vs Distraction VR therapy

Exploratory Outcome: Depression over time as measured by PROMIS Depression (version 4)

Hypothesis: Skills-based VR will lead to a greater improvement in PROMIS Depression than distraction-based VR or Sham VR.

Comparisons: Superiority for both of the following (1) Distraction VR therapy vs. sham VR therapy; (2) skills-based VR therapy vs. sham VR therapy, if there is a statistically significant difference in Skills based VR vs Sham VR then a third test will be completed (3) Skills-based VR therapy vs Distraction VR therapy

Exploratory Outcome: Increased physical function over time as measured by total steps using biometric data

Hypothesis: Skills-based VR will lead to a greater improvement in physical activity than distraction-based VR or Sham VR.

Comparisons: Superiority for both of the following (1) Distraction VR therapy vs. sham VR therapy; (2) skills-based VR therapy vs. sham VR therapy, if there is a statistically significant difference in Skills based VR vs Sham VR then a third test will be completed (3) Skills-based VR therapy vs Distraction VR therapy

Exploratory Outcome: Improvement in physical function as measured by PROMIS physical function (version 6b)

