Hypothesis: Skills-based VR will lead to a greater improvement in physical activity than distraction-based VR or Sham VR.

Comparisons: Superiority for both of the following (1) Distraction VR therapy vs. sham VR therapy; (2) skills-based VR therapy vs. sham VR therapy, if there is a statistically significant difference in Skills based VR vs Sham VR then a third test will be completed (3) Skills-based VR therapy vs Distraction VR therapy  
See Section 4.6.3 of the SAP for details on the assessment of each the above outcomes.

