#### **4.4 Demographic and Baseline Characteristics**

We will summarize demographic and baseline characteristics both by treatment group and overall. Any time-to-event counts will be measured from the day of randomization. Body Mass Index (BMI) will be calculated according to:  $BMI = \text{weight (kg)} / (\text{height (m)})^2$ . Age will be calculated according to:  $Age = (\text{date of event} - \text{birth date} + 1) / 365.25$ . Weekly average opioid dosage will be calculated as a 7-day average of daily maximum milligrams morphine equivalent (MME) as prescribed. Mean activity measures will be calculated as weekly averages (e.g. weekly steps, weekly sleep minutes). Activity classification (i.e. sedentary versus light versus moderate, etc.) will be provided by FitBit and reported as such. Zip code will be matched to median income using census data as an aggregate measure of socio-economic status.

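### The protocol names two Fitbit sleep measures, but the SAP section it points to models only minutes asleep, so sleep efficiency has no planned analysis

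*SAP*

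**What the plan says.** The protocol synopsis (1.1) lists a tertiary objective on "improving wearable measures of sleep quality from baseline to Day 90". The objectives table in Protocol Section 3 words the objective as wearable measures of sleep and gives the endpoint as "sleep quantity (total minutes asleep as well as 'sleep efficiency', see Section 4.6.3 for more info". Protocol 9.4.9 lists the exploratory outcome as "Quality of sleep over time by biometric data on Fitbit Charge 4 (total minutes asleep and sleep efficiency per night", commits to comparing each VR arm with sham, and closes with "See Section 4.6.3 of the SAP for details on the assessment of each the above outcomes".

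SAP 4.6.3 (Exploratory Endpoint Analyses, Biometric Data – Sleep) states "The repeated measures are the change from baseline weekly minutes classified as" sleep, at weekly intervals to Day 90. On covariates it says "The model will include fixed categorical effects for treatment, week, and baseline weekly steps as a continuous covariate". SAP 4.4 says "Mean activity measures will be calculated as weekly averages (e.g. weekly steps, weekly sleep minutes", and Protocol 9.4.5 has the same rule. The SAP 3.2 table of objectives and endpoints lists Fitbit steps but no Fitbit sleep endpoint.

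**The concern.** The protocol hands the analysis of both sleep measures to the SAP, and the SAP specifies only one. An analyst who follows the SAP leaves sleep efficiency out. One who follows the protocol has to choose its definition, time unit, baseline and model without a written rule, possibly after seeing the data.

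Protocol Section 3 counts the objective as achieved on statistical evidence of measured improvement in either VR arm, and does not say which measure decides. With one measure specified and the other not, the reported basis for that objective could be settled after the fact.

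**Working it through.** No sample size, power or error-rate figure is involved, so the check is a comparison of the text in each place.

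| Place | Fitbit sleep measure(s) named | Time unit | Analysis given |
|---|---|---|---|
| Protocol 1.1 | sleep quality, no measure named | none | none |
| Protocol 3 | minutes asleep; sleep efficiency | none | refers to Section 4.6.3 |
| Protocol 9.4.5 | sleep minutes | weekly average | derivation only |
| Protocol 9.4.9 | minutes asleep; sleep efficiency | per night | arm comparisons named; refers to SAP 4.6.3 |
| SAP 3.2 (objectives table) | none | – | – |
| SAP 4.4 | sleep minutes | weekly average | derivation only |
| SAP 4.6.3 (Exploratory, Sleep) | sleep minutes | weekly | repeated-measures mixed model |
| SAP 4.6.3 (Subgroup Analyses) | none | – | – |

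1. **Where the reference leads.** The protocol has no Section 4.6.3 of its own (its Section 4 ends at 4.4), and 9.4.9 says that the SAP section is meant. Two SAP sections carry the number 4.6.3. Neither mentions sleep efficiency.
2. **Count.** The protocol names 2 measures and the SAP models 1, so 2 − 1 = 1 named measure has no model in either document.
3. **Oversight or decision?** SAP 5.2, where departures from the protocol's planned analyses belong, holds only a placeholder. The sleep paragraph closely follows the steps paragraph before it and still adjusts for baseline weekly steps. That looks more like text not adapted to the outcome than a choice to drop efficiency, though the documents do not settle it.
4. **Time unit.** Protocol 9.4.9 is per night, while Protocol 9.4.5, SAP 4.4 and SAP 4.6.3 are weekly. If all seven nights are recorded, a weekly total is 7 times the nightly mean and the choice is only a rescaling. If the weekly figure is a sum and only k nights are recorded, the total falls to k/7 of its full value with no change in sleep: 6/7 = 86%, 5/7 = 71%, 4/7 = 57%. The documents do not say whether the weekly figure is a sum or a mean over recorded nights.
5. **Baseline.** Protocol 9.4.1 sets baseline at the screening week, Day -8 to Day -2, unless specified otherwise. The Schedule of Activities has the kit received at Day -1 to 0 and Fitbit wear starting at Day 1. No Fitbit value is therefore scheduled within the default baseline window, and no other window is given for sleep. A second sleep model would inherit this gap and the steps covariate.

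**The case against.** The strongest reply is that little depends on this. The endpoint is tertiary/exploratory, SAP 6.3 places exploratory tests outside the gatekeeping, and no success criterion for the trial uses it. Protocol 9.4.9 already commits to between-arm comparisons for this outcome, so what is missing is the specification rather than the intention. Weekly minutes also follow the protocol's own derivation rule in 9.4.5. All of this stands, and it limits the point to a reconciliation of the two documents.

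A reader might go further and infer that the trial's sleep-quality objective would be judged on sleep quantity alone. The documents do not support that, for three reasons.

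- The labels are not consistent. The synopsis and 9.4.9 speak of sleep quality, but the Section 3 table files both minutes and efficiency under sleep quantity. Nothing in either document designates efficiency as the quality component.
- Self-reported sleep quality is a separate secondary objective measured by PROMIS Sleep Disturbance, with a specified model in Protocol 9.4.3 and SAP 4.6.2. It is untouched by this gap.
- Minutes and efficiency could move in different directions, because minutes asleep can rise simply with longer time in bed. The documents define no efficiency formula and give no time-in-bed figures, so the likelihood or size of such a divergence in this trial cannot be stated.

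What survives under any label is that a measure named twice in the protocol has no analysis in the SAP section meant to hold it.

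**Conclusion.** The point holds as a mismatch between the documents: one of two protocol-specified wearable sleep measures, sleep efficiency, would not be compared between arms if the SAP is run as written, and the SAP objectives table omits the wearable sleep endpoint altogether. It is minor. Primary and secondary conclusions, including self-reported sleep, are unaffected.

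The conclusion rests on reading the Section 4.6.3 reference as the SAP section, which 9.4.9 confirms, and on the SAP supplied being the one in force. It needs no assumption about how Fitbit defines efficiency.

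**What to change.** In SAP 4.6.3 (Biometric Data – Sleep):

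- Add sleep efficiency as a second modelled exploratory outcome and write down its derivation. First confirm that the export supports it: Protocol 8.2.1 and 10.1.9.1 describe day, hour and minute data but mention neither efficiency nor time in bed.
- Use each measure's own baseline sleep value as covariate, in place of baseline weekly steps.
- State the baseline window for Fitbit sleep, given that wear is scheduled from Day 1.

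Elsewhere:

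- Add the wearable sleep endpoint to the SAP 3.2 table.
- Use one time unit in Protocol 9.4.5, Protocol 9.4.9 and SAP 4.6.3. A mean over recorded nights avoids the k/7 effect shown above.
- Report minutes asleep and sleep efficiency separately under their own names, and do not read minutes alone as evidence of sleep quality.

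Removing efficiency from the protocol would also reconcile the texts, but at the price of a measure the protocol has already named. The cost of the proposed change is one extra exploratory model plus wording in both documents. It adds no data collection if the export check succeeds.

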### 9.4 STATISTICAL ANALYSES

#### 9.4.1 GENERAL APPROACH

All statistical analyses will be performed jointly by the Cedars-Sinai Biostatistics Core and the Cedars-Sinai Center for Outcomes Research and Education (CS\_CORE) using SAS® software version 9.3 or higher (SAS Institute, Cary, NC, USA), R pack3.5.0 (R Foundation for Statistical Computing, Vienna, Austria) or Stata software version 14 or higher (StataCorp LLC, College Station, TX, USA).

Continuous variables will be summarized using descriptive statistics (N, mean, standard deviation, minimum, median, and maximum). Categorical variables will be summarized using the number and percentage of patients in each category. Data will be summarized with respect to patient demographic and baseline characteristics both across the study and by study-arm. The efficacy endpoints, safety assessments, and other outcome results for each treatment group will be summarized descriptively unless otherwise indicated. In addition, statistical model estimates of least squares means, treatment differences, p-values and 95% confidence intervals will also be provided where relevant. The fit of linear models will be assessed using residual plots and/or other diagnostic plots as appropriate. The fit of logistic models will be assessed using Hosmer-Lemeshow goodness-of-fit and/or receiver operating characteristic (ROC) curves as appropriate. All statistical tests will be 2-sided and performed at the 0.05 level of significance unless stated otherwise. Baseline is defined as the value at the screening week (Day -8 to Day -2) for all parameters, unless specified otherwise.

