#### 9.4.5 BASELINE DESCRIPTIVE STATISTICS

We will summarize demographic and baseline characteristics both by treatment group and overall. Any time-to-event counts will be measured from the day of randomization. Body Mass Index (BMI) will be calculated according to:  $BMI = \text{weight (kg)} / (\text{height (m)})^2$ . Age will be calculated according to:  $Age = (\text{date of event-birth date} + 1) / 365.25$ . Weekly average opioid dosage will be calculated as a 7-day average of daily maximum milligrams morphine equivalent (MME) as prescribed. Mean activity measures will be calculated as weekly averages (e.g. weekly steps, weekly sleep minutes). Activity classification (i.e.

sedentary versus light versus moderate, etc.) will be provided by FitBit and reported as such. Zip code will be matched to median income using census data as an aggregate measure of socio-economic status.

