## 4. STATISTICAL ANALYSES

### 4.1 General Methodology

All statistical analyses will be performed jointly by the Cedars-Sinai Biostatistics Core and the Cedars-Sinai Center for Outcomes Research and Education (CS\_CORE) using SAS® software version 9.3 or higher (SAS Institute, Cary, NC, USA), R pack 4.1.1 (R Foundation for Statistical Computing, Vienna, Austria) or Stata software version 14 or higher (StataCorp LLC, College Station, TX, USA).

Continuous variables will be summarized using descriptive statistics (N, mean, standard deviation, minimum, median, and maximum). Categorical variables will be summarized using the number and percentage of patients in each category. Data will be summarized with respect to patient demographic and baseline characteristics both across the study and by study-arm. The efficacy endpoints, safety assessments, and other outcome results for each treatment group will be summarized descriptively unless otherwise indicated. In addition, statistical model estimates of least squares means, treatment differences, p-values and 95% confidence intervals will also be provided where relevant. The fit of linear models will be assessed using residual plots and/or other diagnostic plots as appropriate. The fit of logistic models will be assessed using Hosmer-Lemeshow goodness-of-fit and/or receiver operating characteristic (ROC) curves as appropriate. All statistical tests will be 2-sided and performed at the 0.05 level of significance unless stated

otherwise. Baseline is defined as the value at the screening week for all parameters, unless specified otherwise.

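### The Fitbit steps and sleep models have no treatment-by-week term, so their Day 90 arm difference is an average over all weeks; the sleep model also adjusts for baseline steps

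*SAP*

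**What the plan says.** SAP 4.6.3, Exploratory Endpoint Analyses, specifies both Fitbit models.

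- **Steps.** The outcome is weekly change from baseline in steps. "The model will include fixed categorical effects for treatment, week, and the baseline weekly steps as a continuous covariate". On inference: "Primary inference will be based on the treatment comparison of least squares means at Day 90 from this model".
- **Sleep.** The outcome is weekly change from baseline in minutes asleep. "The model will include fixed categorical effects for treatment, week, and baseline weekly steps as a continuous covariate". The promised output includes "treatment differences in least squares means, and 95% confidence intervals for each time point", and the only p-value is at Day 90.

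The SAP's other repeated-measures models are the primary PROMIS-PI model (4.6.1), the four secondary models (4.6.2), and PROMIS-PF and PROMIS-Depression (4.6.3). All of them carry the interaction and the baseline of their own outcome. PROMIS-Depression, for example: "The model will include fixed categorical effects for treatment, week, treatment by week interaction, and the baseline PROMIS-Depression score as a continuous covariate".

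Protocol 9.4.9 gives no other model for steps or sleep and refers the reader to SAP 4.6.3.

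**The concern.** The fixed-effects sentence and the output sentence cannot both be honoured in any useful sense. Weekly differences can be printed from the additive model, but they are one number repeated, and the interval labelled Day 90 describes that pooled number.

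At stake is whether the steps and sleep objectives, which the protocol and SAP define as change to Day 90, are judged on Day 90 at all. A growing effect would generally be understated. An effect that had worn off could be reported as present at Day 90.

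A constant effect cannot be taken for granted here. The skills program runs 56 days (Protocol 4.3 and 6.1.1). Protocol 6.1.2 ends the daily-use instruction after eight weeks, while 4.3 describes continued daily use. Those two passages must be reconciled in their own right.

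Separately, the sleep model adjusts for the baseline of a different variable. This looks like a carry-over from the steps paragraph.

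**Working it through.** **Inputs.** From the SAP: the fixed effects listed above, 120 per arm (3.3), and two-sided 0.05 (4.1). Inferred: 13 weekly measurements (90/7 = 12.9). Assumed, because the documents give no Fitbit SD, correlation, effect size or power: unit SD in every week, exchangeable correlation r or AR(1) correlation ρ, and the effect shapes below. There is no figure in the plan to reproduce.

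**1. Structure.** As written, the mean for arm a in week k is μ_k + τ_a + β × baseline. The arm difference is τ_a − τ_sham, which does not depend on k under any covariance structure. In one simulated fit (120 per arm, effect rising from 0 to 1) the additive model gave 0.542 in all 13 weeks. With the interaction, the same data gave −0.09 in week 1 and 0.83 in week 13.

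**2. What the single parameter estimates, no baseline term.** The weights are w = S⁻¹1 / (1′S⁻¹1), where S is the within-patient covariance. Exchangeable correlation gives equal weights. AR(1) gives relative weight 1 to the first and last weeks and 1 − ρ to the 11 between.

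- *Linear growth, k/13, true Day 90 = 1:* (1 + … + 13)/13² = 91/169 = 0.54. AR(1) gives the same value by symmetry.
- *Held at 1 to week 8, then 0.8, 0.6, 0.4, 0.2, 0, true Day 90 = 0:* exchangeable 10/13 = 0.77. AR(1) gives [1 + 9(1 − ρ)] / [2 + 11(1 − ρ)]: 5.5/7.5 = 0.73, 3.7/5.3 = 0.70 and 1.9/3.1 = 0.61 at ρ = 0.5, 0.7 and 0.9.
- *Constant effect:* no error.

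**3. With the outcome's own baseline as covariate (the steps model).** S is replaced by R = S − b(c1′ + 1c′) + b²11′, where c holds each week's correlation with baseline and b is the common slope. Exchangeable weights stay equal. Under AR(1), early weeks gain weight:

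| ρ | growth (truth 1) | held then gone (truth 0) |
|---|---|---|
| 0.5 | 0.510 | 0.750 |
| 0.7 | 0.430 | 0.769 |
| 0.8 | 0.339 | 0.811 |
| 0.9 | 0.205 | 0.893 |

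For sleep as written (change score, baseline steps assumed unrelated to it), ρ = 0.5, 0.7 and 0.9 give growth 0.308, 0.215 and 0.123, and held-then-gone 0.867, 0.909 and 0.961. The SAP covariance is unstructured, so the real weights cannot be known in advance.

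**4. Precision of the week-13 contrast against the pooled average, baseline covariate included.** For exchangeable r, the pooled variance is (1 + 12r)/13 − r² and the week-13 variance is 1 − r². The AR(1) values come from R numerically. Power is Φ(d/√(2v/120) − 1.96) with d = 0.3 SD; under growth the pooled d is 0.3 times the value in step 2 or 3.

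| Assumed | v pooled | v week 13 | ratio | power, constant effect | power, growing effect |
|---|---|---|---|---|---|
| exch. 0.5 | 0.288 | 0.750 | 2.6 | 0.99 → 0.76 | 0.64 → 0.76 |
| exch. 0.7 | 0.233 | 0.510 | 2.2 | >0.99 → 0.90 | 0.74 → 0.90 |
| AR(1) 0.5 | 0.188 | 1.016 | 5.4 | >0.99 → 0.64 | 0.78 → 0.64 |
| AR(1) 0.6 | 0.219 | 1.042 | 4.8 | >0.99 → 0.62 | 0.67 → 0.62 |
| AR(1) 0.7 | 0.245 | 1.107 | 4.5 | >0.99 → 0.60 | 0.52 → 0.60 |
| AR(1) 0.9 | 0.170 | 1.237 | 7.3 | >0.99 → 0.55 | 0.21 → 0.55 |

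**5. Sleep covariate.** A change score without its own baseline has single-week variance 2(1 − r), against 1 − r² with it. The ratio is 2/(1 + r) = 1.33 at r = 0.5 and 1.18 at r = 0.7. The pooled sleep model as written has variance (1 − r) × 14/13, that is 0.538 and 0.323. Both repairs together therefore cost 0.750/0.538 = 1.39 and 0.510/0.323 = 1.58. The same ratio under AR(1) 0.5, 0.7 and 0.9 is 1.27, 2.05 and 6.31.

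**The case against.** The best defence is that this is a drafting slip. The output sentences copy the sibling models, so an analyst would probably notice the conflict and add the interaction. An average over follow-up is also a legitimate quantity, and step 4 shows it is estimated much more precisely. The effect shapes above are chosen rather than documented, and a constant effect produces no error. All of this stands, and it limits the weight of the point. It does not remove it: the text leaves the choice open, and the choice would be made with data in hand.

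Three stronger readings are tempting and are not supported.

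- *Adjusting sleep for baseline steps biases the sleep comparison.* It does not. Baseline steps are independent of arm by randomisation, so only precision and adjustment for chance imbalance in baseline sleep are lost.
- *The trial's main conclusions are affected*, because Protocol 4.1 and SAP 3.1 mention biometric outcomes in the primary hypothesis. Success is defined on PROMIS-PI alone, steps and sleep are exploratory, and SAP 6.3 places exploratory tests outside the gatekeeping.
- *No valid Fitbit baseline exists.* A reader might infer this from "Baseline is defined as the value at the screening week (Day -8 to Day -2) for all parameters, unless specified otherwise" set beside a schedule in which the kit arrives at enrollment. But that rule allows exceptions, and the line "Mean activity measures will be calculated as weekly averages (e.g. weekly steps, weekly sleep minutes" says how activity is averaged, not when baseline is taken. The schedule tables are damaged in the available text, and the operating manual was not available. No finding is made on this.

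**Conclusion.** The inconsistency is certain from the text: both Fitbit models force one arm difference across all weeks while promising week-specific differences and a Day 90 test, and the sleep model uses the wrong variable's baseline. The size is conditional. The error at Day 90 is nil for a constant effect. With constant variance, a true value of 1 reached by linear growth is reported as 0.54 (no baseline term) or 0.51 to 0.21 (AR(1) 0.5 to 0.9 with the covariate). A true value of 0 after early benefit is reported as 0.61 to 0.77, or 0.75 to 0.89 with the covariate. These figures rest on 13 weeks and on assumed correlations and shapes. Primary and secondary conclusions are untouched, so severity is minor.

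**What to change.** In SAP 4.6.3, add the treatment-by-week interaction to the steps and sleep models and take the final-week contrast as the Day 90 comparison, in line with the other repeated-measures models. In the sleep model, replace baseline weekly steps with baseline weekly sleep minutes. This is a wording change that needs no new data and adds 24 fixed effects (2 arms × 12 weeks).

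The price is precision. The variance of the steps contrast rises 2.2 to 2.6 times (exchangeable 0.7 to 0.5) or 4.5 to 7.3 times (AR(1) 0.5 to 0.9). Power for a constant 0.3 SD effect falls from about 0.99 to about 0.55 to 0.90. For an effect growing to 0.3 SD, power rises under exchangeable correlation or AR(1) 0.7 and above, but falls under AR(1) 0.5 (0.78 to 0.64) and 0.6 (0.67 to 0.62). The two sleep repairs together cost 1.4 to 1.6 times in variance (exchangeable) or 1.3 to 6.3 times (AR(1)).

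If the sponsor prefers the precision of the additive model, an equally coherent repair is to keep it, call the result an average difference over follow-up, and delete the per-time-point and Day 90 wording. The sleep covariate should be corrected either way.
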